Open Sessions.....	5
Closed Sessions	5
DSMB Reports	5
Formal Minutes.....	5
DSMB Communication of Recommendations	5
Sponsor’s Response to DSMB Recommendations	5
DSMB Closeout.....	6
Confidentiality	6

DSMB Description

The Data and Safety Monitoring Board (DSMB) for the Prevention And Treatment of COVID-19 with Hydroxychloroquine (PATCH) trial has been selected by the Sponsor-Principal Investigator [name] and acts in an advisory capacity to [name] for the PATCH trial to monitor participant safety, data quality and evaluate the progress of the study.

- This DSMB will consist of 5 members:
 - [name], expertise in Emergency medicine, Chair of DSMB
 - [name], expertise in infectious disease
 - [name]: expertise in biostatistics,
 - [name]: expertise in clinical trials and therapeutics
 - [name]: expertise in clinical trials and cardiology
- This DSMB will be independent of the Sponsor, regulatory agencies, IRBs/ECs, and investigators.

DSMB Membership

Requirements for Membership

- Each member declares any conflicts of interest related to the study. Members will notify Sponsor of any change in conflict.
- Each DSMB member maintains confidentiality of DSMB communications.

Remuneration

No remuneration will be provided

Roles and Responsibilities

The primary charge of the DSMB is to monitor the study for subject safety. Formal DSMB safety reviews occur as outlined in the charter. Additional review may be required. The DSMB may monitor effectiveness outcomes to determine relative risk/benefit, futility, or for early termination due to overwhelming effectiveness.

The primary safety endpoint as well as guidance for the conduct of analyses and guidelines/stopping rules are established in the protocol and are reviewed by the DSMB.

The DSMB may also review data related to study conduct. Data to be reviewed and listed in the DSMB reports may include: enrollment rates over time, time from last subject enrolled to date of report (indication of delay between treatment or follow-up and reporting), summary of protocol violations as specified in monitoring reports generated by the Office of Clinical Research (OCR), completeness of treatment and follow-up visit data, and follow-up duration for the population included in the report. Protocol deviations, SAE reports, and assistance in day to day medical decision making on study participants will be handled by the Medical Monitor [name] who is also a member of the DSMB. The DSMB will in turn be able to review formal reports generated by the OCR monitor and the interim analysis reports generated by the Sponsor-Investigator and his team.

The DSMB:

- Meets as outlined in this charter
- Provides recommendations about continuing, modifying, and stopping the study
- Operates according to the procedures described in this charter

Conflicts of Interest

Members comply with the conflict of interest policies specified by [University of Pennsylvania](#) to ensure members do not have serious scientific, financial, personal, or other conflicts of interest related to the conduct, outcome, or impact of the study according to the guidelines specified below (e.g., engaged in any simultaneously occurring competitive trials in any role that could pose a conflict of interest for this study).

The DSMB follows [42 C.F.R. Part 50, Subpart F](#) and Responsible Prospective Contractors [45 C.F.R. Part 94](#).

As determined by the Sponsor, conflicts of interest and/or potential conflicts of interest are mitigated to the greatest extent, consistent with assembling a highly competent DSMB.

DSMB Meetings

First Meeting

The purpose of the first meeting is to review, discuss, and make recommendations about the Charter and protocol. In addition, a chairperson is elected.

Subsequent Meetings

The DSMB meets and reviews unblinded deidentified data provided in the form of a report generated by the sponsor at the timepoints detailed below. The unblinded assignments of subjects may only be shared with the minimum number of study team members needed to generate the report for the DSMB review.

Additional meetings or conference calls are scheduled as needed.

Substudy 1:

1. Substudy 1 Interim analysis 1: after 34 out of a target 100 evaluable patients have completed the study and the report is available for review
2. Substudy 1 Interim analysis 2: after 68 out of a target 100 evaluable patients have completed the study and the report is available for review

Substudy 3

1. Substudy 3 Interim analysis 1: after 50 out of a target 200 evaluable patients have completed the study and the report is available for review
2. Substudy 3 Interim analysis 2: after 100 out of a target 200 evaluable patients have completed the study and the report is available for review

This DSMB is coordinated by the Sponsor. DSMB meetings are held by teleconference. All three members of the DSMB must be present to hold a DSMB meeting. Critical decisions of the DSMB are made by unanimous vote whenever possible, or majority vote if this is not possible.

While the Medical Monitor will review deviations, unanticipated serious adverse events and safety data, she may consult the DSMB as needed.

Meeting Format

DSMB meetings are organized into open and closed sessions. Data reviewed by the DSMB is provided by the Sponsor.

Open Sessions

Data presented in the open session may include enrollment data, individual adverse event data, baseline characteristics, overall data accuracy and compliance data or issues, and other administrative data. The DSMB also considers data from other studies or external sources as made available during its deliberations.

During the open sessions, prepared summary reports and tables are reviewed and discussed by the DSMB.

Facilitator(s) (e.g., member of Sponsor and/or investigator team responsible for the report preparation) and observers from University research oversight committees may attend the DSMB meeting Open Sessions as necessary in order to facilitate data presentation, follow-up reporting, and answer questions posed by the DSMB.

Closed Sessions

The closed session is restricted to the DSMB members. Data which may compromise the integrity of the study (e.g., comparative data) is analyzed and discussed only in the closed session. Details of closed session deliberations (e.g., minutes) are considered privileged and not subject to disclosure except as required by law.

Meetings conclude with a recommendation to continue, modify, pause, or terminate the study. In addition, recommendations for modification, pause, or termination may be endorsed for perceived safety concerns based on clinical judgment.

DSMB Reports

Formal Minutes

Minutes of the open session are recorded and finalized. Minutes are approved by the chairperson and maintained by the Sponsor.

The minutes of the closed session are recorded. They are stored in a secure location by the DSMB chair, separately from the minutes of the open session. Once finalized and approved by the DSMB chair, they will be retained until the trial is completed.

DSMB Communication of Recommendations

A formal report containing the recommendations of the study is sent to the Sponsor. If the DSMB recommends continuation of the study, the minutes and report for continuation are shared with the Sponsor no later than 3 business days after the meeting.

If the DSMB recommends modifications, pause, or termination of the study, the minutes and report are shared with the Sponsor no later than 1 business days after the meeting.

In addition, any findings that are considered to be serious and potentially consequential that require immediate action are promptly shared with the Sponsor.

Sponsor's Response to DSMB Recommendations

The Sponsor reviews and responds to the DSMB recommendations.

DSMB Closeout

This study may be terminated under a variety of circumstances including, but not limited to, termination for overwhelming effectiveness, futility, or safety issues per protocol, poor enrollment, or DSMB monitoring guidelines.

Confidentiality

All data provided to the DSMB and all deliberations of the DSMB are privileged and confidential. The DSMB agrees to use this information to accomplish the responsibilities of the DSMB and will not use it for other purposes without written consent from the Sponsor.

**The PATCH (Prevention And Treatment of COVID-19 with HCQ) Trial:
A 3 Arm Randomized Trial of Hydroxychloroquine in the Prevention and Treatment of COVID-19**

Sponsor-Investigator/ Principal Investigator:	[name] (Medicine) University of Pennsylvania Perelman School of Medicine Department of Medicine, Division of Hematology Oncology [name] [contact]
Primary Emergency Medicine Sub-Investigator	[name] (Emergency Medicine) University of Pennsylvania Perelman School of Medicine Department of Emergency Medicine Hospital of the University of Pennsylvania Emergency Department, [name] [contact]
Primary Infectious Diseases Sub-Investigator	[name] [name] [contact]

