8.2 Dose Delays

Major Events are grade 3 and 4 hematologic and non-hematologic toxicities that are not treatment -related. Treatment should be delayed for major events if HCQ may further complicate the non-treatment related event. If a major event requires a delay of treatment, treatment must be delayed until toxicity is resolved (\leq Grade 2 or \leq Baseline). For treatment-related toxicities and major events, if toxicity is not resolved in \leq 14 days, patient will be taken off treatment unless there is an exception granted by the medical monitor.

8.3 Ocular toxicity. The only toxicity that requires discontinuation of HCQ is retinopathy. Published literature indicates HCQ retinopathy is idiosyncratic and is uncommon in patients receiving HCQ for less than a few years. Our ongoing study of dabrafenib, trametinib, and HCQ (BAMM; NCTNCT02257424) found no clinically meaningful ocular toxicity in 10 patients studied extensively with serial ocular exams (25). Although HCQ retinotoxicity can occur at shorter than expected intervals with the use of high dose (>5 mg/Kg/day of real body weight) treatment protocols, the cumulative doses required to elicit a retinopathy were only reached after about a year of treatment (26). Thus, we do not anticipate cumulative doses in this trial will reach retinotoxic levels (>200 grams) and have, therefore, not included mandatory ocular exams in this protocol. However, participant will be advised to report with any visual changes at which point a comprehensive ophthalmic exam will take place to decide whether HCQ should be permanently discontinued. As a precaution, patients with renal failure will also be excluded from the trial.

Laboratory monitoring is not recommended for HCQ use in rheumatoid arthritis. The American College of Rheumatology guidelines for the treatment of rheumatoid arthritis recommends no laboratory testing for outpatients that are started on hydroxychloroquine (27). HCQ doses for rheumatoid arthritis range from 400mg daily to 400mg twice a day encompassing the dosing paradigms in Sub-study 1 and sub-study3.

8.3 Safety of HCQ in pregnancy obviates the need for pregnancy monitoring. Numerous case series and a recent large scale epidemiological study demonstrate the safety of HCQ in outpatient pregnant women with systemic lupus erythematosus (28). Therefore we are not requiring pregnancy test prior to starting HCQ in sub-studies 1 and 3. Potential participants that are known to be pregnant are excluded.

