11.5 Data Safety and Monitoring Board (DSMB)

DSMB Description

The Data and Safety Monitoring Board (DSMB) for the Prevention And Treatment of COVID-19 with Hydroxychloroquine (PATCH) trial has been selected by the Sponsor-Principal Investigator [name] and acts in an advisory capacity to [name] for the PATCH trial to monitor participant safety, data quality and evaluate the progress of the study. Operational details of the DSMB are provided in the PATCH trial DSMB Charter.

- This DSMB will consist of 5 members with expertise in statistics, clinical trials, infectious disease, cardiology. The DSMB chair may change the membership of the DSMB in consultation with the PI.
- Observers from other research committees at PENN can be invited to join the open session of the DSMB deliberation.
- This DSMB will be independent of the Sponsor, regulatory agencies, IRBs/ECs, and investigators.

Roles and Responsibilities

The primary charge of the DSMB is to monitor the study for subject safety. Formal DSMB safety reviews occur as outlined in the charter. Additional review may be required. The DSMB may monitor effectiveness outcomes to determine relative risk/benefit, futility, or for early termination due to overwhelming effectiveness.

The PATCH Trial

The primary safety endpoint as well as guidance for the conduct of analyses and guidelines/stopping rules are established in the protocol and are reviewed by the DSMB.

The DSMB may also review data related to study conduct. Data to be reviewed and listed in the DSMB reports may include: enrollment rates over time, time from last subject enrolled to date of report (indication of delay between treatment or follow-up and reporting), summary of protocol violations as specified in monitoring reports generated by the Office of Clinical Research (OCR), completeness of treatment and follow-up visit data, and follow-up duration for the population included in the report. Protocol deviations, SAE reports, and assistance in day to day medical decision making on study participants will be handled by the Medical Monitor [name] who is also a member of the DSMB. The DSM will in turn be able to review formal reports generated by the OCR monitor and the interim analysis reports generated by the Sponsor-Investigator and his team.

The DSMB:

- Meets as outlined in this charter
- Provides recommendations about continuing, modifying, and stopping the study
- Operates according to the procedures described in this charter

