All adverse events occurring during the study period must be recorded. Adverse events will be measured and graded in accordance with the CTCAE v 5.0. The clinical course of each event should be followed until resolution, stabilization, or until it has been determined that the study treatment or participation is not the cause. Serious adverse events that are still ongoing at the end of the study period must be followed up to determine the final outcome. Any serious adverse event that occurs after the study period and is considered to be at least possibly related to the study treatment or study participation should be recorded and reported immediately.

Serious Adverse Events

Adverse events are classified as serious or non-serious.

A serious adverse event is any AE that is:

- fatal
- life-threatening
- requires or prolongs hospital stay
- results in persistent or significant disability or incapacity
- a congenital anomaly or birth defect
- Suspected transmission of an infectious agent (eg, pathogenic or nonpathogenic) via the study drug is an SAE.
- an important medical event

Important medical events are those that may not be immediately life threatening, but are clearly of major clinical significance. They may jeopardize the participant, and may require intervention to prevent one of the other serious outcomes noted above. For example, drug overdose or abuse, a seizure that did not result in in-patient hospitalization, or intensive treatment of bronchospasm in an emergency department would typically be considered serious. Theft, sale, or use of the study product by any person other than the participant will be reported as a medically important event.

DSMB Description

The Data and Safety Monitoring Board (DSMB) for the Prevention And Treatment of COVID-19 with Hydroxychloroquine (PATCH) trial has been selected by the Sponsor- Principal Investigator [name] and acts in an advisory capacity to [name] for the PATCH trial to monitor participant safety, data quality and evaluate the progress of the study.

The DSMB will consist of 5 members:

[name], expertise in Emergency medicine, Chair of DSMB

[name], expertise in infectious disease

[name]: expertise in biostatistics,

[name]: expertise in clinical trials and therapeutics

[name]: expertise in clinical trials and cardiology

This DSMB will be independent of the Sponsor, regulatory agencies, IRBs/ECs, and investigators.

DSMB Membership

Requirements for Membership

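### The Medical Monitor takes part in trial conduct and also sits, with no stated recusal, on the DSMB that reviews comparative unblinded data; separately, the quorum sentence says three for a board of five

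*Protocol*

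**What the plan says.** **Role in conduct.** Protocol section 11.5, the DSMB Charter (Roles and Responsibilities) and the SAP (same heading) carry one arrangement. Protocol deviations, SAE reports and "assistance in day to day medical decision making on study participants will be handled by the Medical Monitor", and the Medical Monitor is a person "who is also a member of the DSMB". Protocol section 8.2 takes a participant off treatment when toxicity has not resolved within 14 days, "unless there is an exception granted by the medical monitor".

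**Role on the board.** The charter and SAP (Subsequent Meetings) have the DSMB review data that are unblinded and deidentified. Under Closed Sessions, attendance is limited to DSMB members, and comparative data are discussed only there. No text limits the Medical Monitor to open sessions or removes the vote.

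**Independence.** The charter states: "This DSMB will be independent of the Sponsor, regulatory agencies, IRBs/ECs, and investigators". Protocol section 11.5 and the SAP (DSMB Description) say the same. Protocol section 11.4 describes the Medical Monitor as an independent clinician. The protocol's title page lists the Medical Monitor apart from the investigators, but in the same division as the sponsor-investigator.

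**Size and quorum.** Protocol section 11.5: "This DSMB will consist of 5 members with expertise in statistics, clinical trials, infectious disease, cardiology". Charter: "This DSMB will consist of 5 members". SAP: "The DSMB will consist of 5 members". Yet the charter and the SAP (Subsequent Meetings) both say: "All three members of the DSMB must be present to hold a DSMB meeting". Critical decisions are unanimous where possible and otherwise by majority.

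**The concern.** A closed session keeps results by arm away from people who act on individual participants. The charter recognises this for the study team: it limits unblinded assignments to the fewest people needed to write the report. The Medical Monitor falls outside that protection. The same person advises on participants, handles deviations and SAE reports, may grant a treatment exception, and as a board member may attend the session where the arms are compared. Advice, exceptions and report handling for later participants could then be influenced, even unintentionally, by knowing which arm is ahead.

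The quorum is a separate defect. Protocol section 13.1 makes the futility boundaries non-binding, so a futility stop rests on judgement informed by the board's recommendation. The second Sub-Study 3 look also evaluates conditional power, with a possible change in sample size. A rule on who must be present for such a review should be one that can be applied.

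**Working it through.** No power, alpha or event figure in the plan is in dispute, so the check is a comparison of texts and a head count.

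**1. Are the two roles held together without a barrier?**
- Conduct: deviations, SAE reports and day-to-day assistance (section 11.5, charter, SAP), plus the exception in section 8.2.
- Oversight: DSMB member, stated in the same sentence.
- Barrier: none stated under Subsequent Meetings or Closed Sessions.
- The charter also says the Medical Monitor may consult the DSMB as needed, which describes someone outside the board. It therefore treats the role as both inside and outside.

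**2. How long does the overlap last?** It starts at the first look.

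- Sub-Study 3, target 200: looks after 50 and 100 completers leave up to 200 − 50 = 150 and 200 − 100 = 100 still to complete.
- Sub-Study 1, target 100: looks after 34 and 68 leave up to 100 − 34 = 66 and 100 − 68 = 32.

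These are upper limits on participants whose follow-up continues after a look. They do not count people affected.

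**3. Does deidentification remove the issue?** Only in part. The stated risk needs knowledge of results by arm, not of individual assignments. Few events are also expected. Under the plan's 10% versus 1% with equal arms:
- at 50 completers, 25 × 0.10 + 25 × 0.01 = 2.75 infections;
- at 100 completers, 50 × 0.10 + 50 × 0.01 = 5.5 infections.

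With so few events, someone who also handles individual SAE reports might recognise a case. That is an inference; the documents do not say so.

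**4. Head count against quorum.** The charter and SAP list emergency medicine (chair), infectious disease, biostatistics, clinical trials and therapeutics, and clinical trials and cardiology: 5. The quorum sentence gives 3.
- If it means every member, the number should be 5, and the biostatistician is always present.
- If it means three of five, a meeting could be valid without the biostatistician. If the majority is then taken among those present, 2 people could carry a critical decision.

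The documents do not settle which reading is meant.

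**5. Effect of removing one vote.** 5 − 1 = 4 voters. A 2–2 split is possible, and the majority rule does not resolve it.

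**The case against.** The best defence is that the documents limit what the Medical Monitor can do and do not make the role part of the sponsor's team. Five stronger readings are tempting, and the texts do not support them.

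- **That the plan contradicts its own independence statement.** The statement names the sponsor, regulators, ethics bodies and investigators. Section 11.4 calls the Medical Monitor independent, and the title page does not list the role among the investigators. This stands. What is left is a conflict of function, made more pointed by the shared division.
- **That SAE attribution could be biased.** Section 11.2 reserves AE grading to the PI and physician sub-investigators and addresses its causality guideline to investigators. The Medical Monitor handles and reviews reports; no text gives the role attribution.
- **That 150 or 100 participants would be managed under unblinded decisions.** The stated role is assistance plus the section 8.2 exception. Discontinuation (section 10.3) rests with investigators and treating physicians; unblinding and crossover (sections 5.0 and 7.5) run through study staff, clinical investigators and the pharmacy.
- **That the primary result is compromised.** The Sub-Study 3 endpoint is PCR positivity, with scheduled swabs processed by an outside laboratory (section 8.4.2). Evaluability starts from baseline PCR status and at least one dose. No Medical Monitor decision is stated to enter the primary analysis.
- **That the quorum rule lets a board meet without its biostatistician.** This follows only if the sentence means three of five.

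It is also fair to say that no text requires the Medical Monitor to be blinded. The case for separating the roles is ordinary monitoring practice, not a rule the plan breaks. The number three may be text left from a smaller board, which is an assumption. None of this supplies a recusal or makes three equal five.

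**Conclusion.** The concern holds as two modest, separate points. First, a person with duties in trial conduct has unrestricted membership of the board that reviews comparative interim data, which weakens the independence the board claims. The exposure runs from the first look to the end of follow-up: at most 150 of 200 participants in Sub-Study 3 and 66 of 100 in Sub-Study 1. Bias is a risk, not something shown, and no alpha, power or primary-endpoint figure changes. Second, the quorum number does not match the board in either the charter or the SAP.

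The first point assumes that board membership carries closed-session access, which is how the charter reads without a recusal. The count of four remaining voters assumes that the Medical Monitor is one of the five listed and, being a clinician, does not hold the biostatistics seat. The public text does not show which seat it is. The change is worth making because it is cheap, not because the result is in doubt.

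**What to change.** Amend Protocol section 11.5, the DSMB Charter and the SAP together, since all three carry the dual-role sentence and the count of five:

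1. The Medical Monitor attends open sessions only, receives no closed report and has no vote. The provision for consulting the DSMB can stay, and would then fit the role.
2. In the charter and SAP, replace the quorum sentence with a number that matches the remaining voting members.
3. Require the biostatistician at any meeting that reviews an interim analysis.
4. State how a tie is resolved.

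The cost is wording and no new staff. The downside is one fewer voting member, leaving four and a possible 2–2 split, which is why item 4 is needed. If a fifth vote is wanted, section 11.5 already lets the chair change the membership in consultation with the PI. The charter also governs Sub-Study 1, which the protocol's introduction describes as still enrolling, so the change can act on any look that remains there.
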